4.3 Exploratory Parameters

1. Plasma volume collected

Statistical summaries (mean, median, and range) will be presented for plasma volumes. Additionally, the collected plasma volumes per procedure and over time for the New Nomogram (Test arm) will be compared to the collected plasma volumes per procedure for the Optimized Nomogram (Control arm). The comparison between the Test arm and the Control arm will be based on a t-test.

2. Collection time

Statistical summaries (mean, median, and range) will be presented for collection time. Additionally, the collection time for the New Nomogram (Test arm) will be compared to the collection time for the Optimized Nomogram (Control arm). The comparison between the Test arm and the Control arm will be based on a t-test.

5 Data Conventions

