This is a multicenter randomized controlled clinical trial to evaluate the Aurora Xi New Nomogram for the collection of plasma. The study is to determine whether the overall rate of significant hypotensive adverse events (SHAEs) in donors using the Aurora Xi New Nomogram is less than double the rate of SHAEs in donors using the Aurora Xi Optimized Nomogram. Randomization will be carried out within blocks of variables size (2, 4, or 6) within centers. Donors will be recruited until outcomes are available for a minimum of 51,720 plasmapheresis procedures (approximately 11,519 individual donors) from three BioLife plasma centers. Donors will be randomized in a 1:1 ratio to donate in procedures under the New Nomogram (Test) or the Optimized Nomogram (Control). Donors will provide donations over an 8-week follow-up period. Subjects will be retained in the assigned study arm (Test/Control) throughout their participation in the study period.

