3.1 Sample Size Determination

The sample size requirement is calculated based on a model for correlated binary data in which the marginal mean is modelled with a log-link function and set by

$$\log \mu_{ij} = \beta_0 + \beta_1 X_i$$

where $X_i = 1$ for an individual assigned to the experimental arm and $X_i = 0$ otherwise. Note that center is not controlled for in the sample size calculation. Controlling for center is anticipated to improve power by explaining variation in the response, so this is a conservative approach to estimating the sample size since the power is anticipated to be at least the desired power. For the sample size derivation, the fitted model uses the identity variance function and a working independence assumption with a robust variance derived from a joint model to account for the association in the responses from serial donations from the same donor. The calculations require specification of the mean $\mu_x = E(Y_{ij}|X_i = x)$ and the variance $V_x = \text{var}(Y_{ij}|X_i = x)$ of the response Y_{ij} to procedure j from donor i as well as the within-donor correlation. If κ_x and μ_x is the mean and variance for the number of procedures for a donor in arm x and n is the total number of donors to be recruited, then the asymptotic (large sample) variance (*asvar*) of the estimator of the log relative rate satisfies

$$\text{asvar} \left\{ \sqrt{n} \left(\hat{\beta}_1 - \beta_1 \right) \right\} \simeq \frac{2V_0}{\kappa_0 \mu_0^2} \left(1 + \frac{\delta_0 \rho}{\kappa_0} \right) + \frac{2V_1}{\kappa_1 \mu_1^2} \left(1 + \frac{\delta_1 \rho}{\kappa_1} \right)$$

where $\delta_x = \nu_x + \kappa_x^2 - \kappa_x$ and ρ is the within-donor correlation in the responses over successive procedures from the same donor. The sample size involves computation of an asymptotic robust variance estimate for the estimator based on a multivariate binary probability mass function with specified marginal event rates of SHAE for the Test and Control arms and a specified exchangeable correlation for responses over successive procedures within the same donor, using the conditional linear family (Preisser and Qaqish, 2014) of multivariate binary models. In addition to the response model, a zero-truncated negative binomial model is used for the number of donation procedures over time from each donor which accommodates between-donor heterogeneity in the procedure rate. The number of required donors is computed based on the constraint

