4.2 Secondary Parameters

Suppose individual i in a sample of size n provides K_i procedures, $i = 1, \dots, n$. Let $Y_{ij} = 1$ if the j th procedure from individual i leads to a SHAE and let $Y_{ij} = 0$ otherwise, $j = 1, \dots, K_i$, $i = 1, \dots, n$. Let $X_i = 1$ if individual i is randomized to the experimental arm and $X_i = 0$ otherwise and let V_i be an additional covariate vector which includes indicators for the sites, and let $Z_i = (X_i, V_i)$. Let $\mu_{ij} = E(Y_{ij})$ denote the mean response for the marginal probability of a SHAE given the full covariate vector Z_i . The event rate is expected to be very low, so in order to estimate the relative risk, the log link function in a generalized linear model (McCullagh and Nelder, 2019) is used in the form of

$$\log \mu_{ij} = \beta_0 + \beta_1 X_i + \beta_2 V_i$$

where $\beta = (\beta_0, \beta_1, \beta_2)$ and the relative rate of a SHAE is $\exp(\beta_1)$ when adjusting for the covariates V_i . Analysis will be carried out based on quasi-likelihood with the identity variance function (Lumley et al, 2006).

The variance function is not the binomial variance function and the responses Y_{ij} , $j = 1, \dots, K_i$ corresponding to the SHAE responses for successive procedures from the same donor are not independent. Therefore, in order to provide protection against a) misspecification of the variance function and b) a working independence assumption for procedures from the same donor, analyses will be based on the generalized estimating equation approach (Liang and Zeger, 1986). A robust variance estimate will be used for inference by defining clusters based on a donor identification variable. Once the above log link model is fitted, the confidence interval approach will be used such that non-inferiority will be claimed if

$$\exp\left(\hat{\beta}_1 + 1.96 s.e.(\hat{\beta}_1)\right) < RR_M$$

where $s.e.(\hat{\beta}_1)$ is the square root of the robust variance estimate.

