For each procedure, the time (in minutes) from the start of plasmapheresis to the first SHAE will be recorded. For procedures not leading to a SHAE, the time will be censored at the time the plasmapheresis is completed. The cumulative incidence function for the time to the first SHAE for a procedure will be estimated for each arm of the study with a gamma distributed random effect used to accommodate a dependence in the time to a SHAE across procedures within the same donor. To estimate the effect of the device on the time to the first SHAE, a stratified Cox regression model will be fitted with a donor-specific gamma distributed random effect (with a mean of 1 and variance ϕ to be estimated) and treatment arm (Aurora Xi New Nomogram or the Aurora Xi Optimized Nomogram), with stratification by center. The exponentiated regression coefficient will give the hazard ratio for the time to the first SHAE per procedure.

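### SAP 4.3 compares plasma volume per procedure by a t-test with no donor adjustment, so its standard error is too small if a donor's volumes are correlated; for collection time no unit of analysis is given

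*SAP*

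**What the plan says.** SAP 4.3 (Exploratory Parameters) covers plasma volume and collection time. For volume, "the collected plasma volumes per procedure and over time for the New Nomogram (Test arm) will be compared" with those of the Control arm. For both measures, "The comparison between the Test arm and the Control arm will be based on a t-test". No donor term, clustering or averaging within donor is mentioned. For collection time the unit of analysis is not stated.

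The SAP's opening description gives the design: donors are randomised 1:1, and "Subjects will be retained in the assigned study arm (Test/Control) throughout their participation in the study period". The target is a "minimum of 51,720 plasmapheresis procedures (approximately 11,519 individual donors) from three BioLife plasma centers".

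Elsewhere the SAP treats repeated procedures as dependent. SAP 3.1 carries a within-donor correlation in the variance, and "a zero-truncated negative binomial model is used for the number of donation procedures over time from each donor". SAP 4.2 states that "SHAE responses for successive procedures from the same donor are not independent" and uses a robust variance clustered on donor. Item 6 of SAP 4.2, on time to first SHAE, has a "gamma distributed random effect used to accommodate a dependence in the time to a SHAE across procedures within the same donor".

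The protocol adds nothing for these two measures. Sections 1 and 3.3 only list the objectives, and sections 12.1 and 12.4 defer the detail of other endpoints to the SAP.

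**The concern.** A two-sample t-test on procedures assumes that every procedure is an independent observation. Here the arm never varies within a donor, so all information about the arm difference lies between donors. If two volumes from the same donor are more alike than volumes from different donors, the test counts more information than the data hold. Its standard error is then too small and its p-value too low.

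Positive correlation is plausible for volume. Protocol section 3 (Background) describes the current US nomogram as weight-based with three tiers, and a donor's weight would usually change little over 8 weeks.

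What is at stake is limited: overstated significance for the reported volume difference, and for collection time if that too is analysed by procedure. Protocol section 12.4.1 speaks of assessing the collection of greater volume, so the volume result is likely to be read as the benefit of the device and deserves a correct standard error.

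**Working it through.** **Inputs from the documents.** Procedures: 51,720. Donors: 11,519. Allocation: 1:1 by donor. SAP 3.1 also gives the control SHAE rate 0.00221, relative rate 1.2, margin 2, 80% power and a two-sided 95% interval. The within-donor correlation of volume or time and the variance of procedures per donor are not given. The SAP states no sample size or precision for the t-tests in 4.3.

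**Step 1: the plan's own figures.** Mean procedures per donor: κ = 51,720/11,519 = 4.49.

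Under independence, the SAP 3.1 formula gives

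N = 2(1.960 + 0.842)² [(1−p₀)/p₀ + (1−p₁)/p₁] / [ln(2/1.2)]²,

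with p₀ = 0.00221 and p₁ = 1.2 × 0.00221 = 0.002652. The bracket is 451.49 + 376.07 = 827.56, so N = 49,784 procedures. The planned 51,720 is 1.039 times this. That is compatible with a small SHAE correlation, about 0.011 if all donors give equal numbers. It cannot be reproduced exactly because the correlation and the count variance are not stated, and nothing here shows it to be wrong. A correlation for a rare binary event is no guide to that of a continuous volume.

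**Step 2: design effect for a procedure-level t-test.** SAP 3.1 multiplies the variance by 1 + δρ/κ, where δ = ν + κ² − κ and ν is the variance of the count k per donor. This equals

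DE = 1 + ρ(E[k²]/E[k] − 1).

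The t-test sets DE to 1. For any ρ > 0 with repeated procedures, DE exceeds 1.

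E[k²]/E[k] for a mean of 4.49 is:
- equal counts: 4.49
- zero-truncated Poisson counts: 5.44
- zero-truncated negative binomial counts (the SAP's own family; size 1.5 is an assumption): 7.36

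**Step 3: consequence.** Ratio of the t-test's standard error to the correct one = 1/√DE. True type I error of a nominal 5% test = 2[1 − Φ(1.96/√DE)]. For example, with ρ = 0.5 and equal counts, DE = 1 + 0.5 × 3.49 = 2.745, the ratio is 0.60 and the type I error is 24%.

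| Assumed ρ | Equal counts: SE ratio, type I | Poisson: SE ratio, type I | Negative binomial: SE ratio, type I |
|---|---|---|---|
| 0.1 | 0.86, 9% | 0.83, 10% | 0.78, 13% |
| 0.3 | 0.70, 17% | 0.65, 20% | 0.59, 25% |
| 0.5 | 0.60, 24% | 0.56, 27% | 0.49, 34% |
| 0.8 | 0.51, 31% | 0.47, 36% | 0.41, 43% |
| 0.95 | 0.48, 35% | 0.44, 39% | 0.38, 46% |

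**Step 4: simulation with no arm difference** (600 donors, 2,000 runs per setting). Counts were either one plus a Poisson variable or geometric capped at 16.

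| ρ | Procedure-level t-test, Poisson type | Procedure-level t-test, geometric |
|---|---|---|
| 0 | 5.7% | 5.0% |
| 0.1 | 10.6% | 12.5% |
| 0.5 | 26.4% | 33.5% |
| 0.8 | 35.3% | 43.7% |

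Across all eight settings, a t-test on donor means rejected 4.5% to 6.2% of the time and a donor-clustered robust test 4.2% to 5.8%. Both remedies hold the nominal level.

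**The case against.** The strongest reply is about reading. The SAP says only that a t-test will be used. The words per procedure stand beside over time, which the SAP does not define, so they may name the quantity (volume per procedure) and not the row of data. A t-test on each donor's mean volume per procedure would fit that reading and would be valid. This is possible, but the SAP nowhere mentions donor means, and the natural reading is a test on procedures. If donor means are intended, one sentence settles it.

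Second, type I error presumes no true difference, while protocol section 9.3 expects some donors to give more plasma than current limits allow. With 51,720 procedures split equally, a procedure-level test calls any difference above 1.96 × √(4/51,720) = 0.017 SD significant. At the most extreme design effect in the table, 7.04, a correct test does so above 0.017 × √7.04 = 0.046 SD. The verdict changes only for an observed difference within that narrow band. This stands, and for volume it makes a false claim of significance less likely in practice. The standard error is still wrong, and a small difference in collection time could be affected if procedures are the unit.

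Third, the correlation and the spread of counts are assumed. That also stands. In addition, 4.49 is a planning average, since protocol section 5.1 allows fewer donors with more procedures each. The direction of the error does not depend on these values; its size does.

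**Conclusion.** The concern holds and is minor. As written, the volume comparison in SAP 4.3 ignores that donors are the randomised unit, and its standard error is too small for any positive within-donor correlation. For collection time the plan is incomplete, and the same error follows if procedures are analysed.

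The table gives the size only under assumed correlations and count distributions. If the correlation were near 0.01, the type I error with equal counts would be 5.4% and the matter negligible. Arm means are unaffected. Both measures are exploratory with no success criterion, so no primary or secondary conclusion changes.

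**What to change.** In SAP 4.3, state the unit of analysis for volume and for collection time, define what over time means for volume, and replace the procedure-level t-test with one of these:

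- an identity-link GEE with working independence, robust variance clustered on donor ID, and site indicators as in the SHAE model; or
- a t-test on one mean per donor.

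The first averages over procedures and the second over donors, so they estimate different quantities and one should be named in advance. A linear mixed model with a donor random effect is also acceptable, but it weights donors in a third way and should be chosen deliberately.

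The cost is one or two sentences and a few lines of SAS. The donor identifier is already needed for SAP 4.2. No new data and no change in sample size are required. Standard errors will be larger if volumes are positively correlated within donor.

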5.1 Data Collection

See Protocol Section 11.

5.2 Data Verification

See Protocol Section 11.

5.3 Data Monitoring

See Protocol Section 11.

5.4 Data Handling

5.4.1 Handling of Missing Data

No missing or incomplete dates will be imputed for this study. No missing or incomplete parameter results will be imputed for this study.

If missing data arises that affects whether an individual donation can contribute to the analyses described that procedure will be excluded in a complete case analysis.

6 Trial Termination Procedures

See Protocol Section 12.

7 Roll-In Analyses

Upon completion of the roll-in procedures at each site (minimum 150 procedures at each clinical site), summary statistics regarding the incidence of adverse events (category and sub-category) will be evaluated by the DSMB. The summary statistics listing will have the randomization category, collection volume at time of adverse event, total plasma volume, and total collection volume fields hidden from reviewers. If deemed acceptable, the study enrollment will remain unaffected and will continue. Roll-in procedures will be included in the evaluable population.

8 Statistical References

Base SAS 9.4 Procedures Guide, SAS Publishing: Cary, NC

9 Randomization Schedule

See Protocol Section 8.

10 Statistical Code for Hypothesis Testing

SAS code will be written to perform hypothesis testing described in Section 4.1. R code is available to perform the sample size estimation described in Sections 3.1 and 4.2. SAS and R codes will be written to generate output. The SAS and R code will be stored on Fresenius Kabi Medical Affairs shared drive.

11 References

1. Lumley T, Kronmal R and Ma S. Relative risk regression in medical research: models, contrasts, estimators, and algorithms. University of Washington Biostatistics Working Paper Series, 7-19-2006.
2. McCullagh P and Nelder JA. *Generalized Linear Models*. Routledge, 2019.
3. Preisser JS and Qaqish BF. A comparison of methods for simulating correlated binary variables with specified marginal means and correlations. *Journal of Statistical Computation and Simulation*, 84(11), 2441-2452, 2014.
4. Seaman S, Pavlou M and Copas A. Review of methods for handling confounding by cluster and informative cluster size in clustered data. *Statistics in Medicine*, 33(30), 5371-5387, 2014.
